1. PROTOCOL SUMMARY

1.1 Schedule of Activities (SoA)

Schedule of activities in Phase 1 portion is described in [Table 1](#); schedule of activities in Phase 2 portion is described in [Table 2](#) and [Table 3](#).

Table 1 Schedule of Activities (Phase 1 portion)

	Screening ^a	Cycle 0		Cycle 1				Cycle 2	Cycle 3	Cycle 4	Cycle 5-12	Cycles 15, 18, 21 and \geq 24 ^b	EoT ^c	Safety Follow Up ^d	Post-treatment disease Follow up ^e	Survival Follow up ^f	Details in Section
		Single dose		Multiple doses													
Day of Each Cycle	-28 to -1	1	2	1	8	15	22	28	15	28	28	28	28				
Visit Window (Days)		0	0	0	± 2	± 2	± 2	± 2	± 2	± 2	± 2	± 2	± 3	+7	+7	± 7	± 7
Informed consent	X																Appendix A3
Hospitalization ^g		From Cycle 0 Day -1 to Cycle 0 Day 2															--
Inclusion/exclusion criteria	X																5.1 & 5.2
Routine clinical procedures																	
Demography	X																8
Medical history	X																8
B symptoms	X							X ^{dd}	X ^{dd}	X ^{dd}	X ^{dd}	Cycle 5, 6, 9 and 12 ^{dd}	Every 12W through Cycle 24, then every 24W thereafter ^{dd}				8.1.4

Table 1 Schedule of Activities (Phase 1 portion)

	Screening ^a	Cycle 0		Cycle 1				Cycle 2		Cycle 3	Cycle 4	Cycle 5-12		Cycles 15, 18, 21 and \geq 24 ^b	EoT ^c	Safety Follow Up ^d	Post-treatment disease Follow up ^e	Survival Follow up ^f	Details in Section
		Single dose		Multiple doses															
Day of Each Cycle	-28 to -1	1	2	1	8	15	22	28	15	28	28	28	28	28					
Visit Window (Days)		0	0	0	± 2	± 2	± 2	± 2	± 2	± 2	± 2	± 2	± 2	± 3	+7	+7	± 7	± 7	
Physical examination ^h	X	X	X	X	X	X	X	X	X	X	X	X	X	X	X	X	X		8.2.2
Vital signs ⁱ	X	X	X	X	X	X	X	X	X	X	X	X	X	X	X	X	X		8.2.3
ECOG status	X	X	X	X	X	X	X	X	X	X	X	X	X	X	X	X	X		8.2.5
ECG ^j	X	X			X		X		X	X	X	X	X	X	X	X	X		8.2.4
Concomitant treatments	←														→				6.5
Routine safety assessments																			
Pregnancy test ^k	X			X	As clinical indicated														8.1.3
Hematology ^l	X	X ^t		X	X	X	X	X	X	X	X	X	X	X	X	X	X		8.1.3
Clinical chemistry ^m	X	X ^t		X	X	X	X	X	X	X	X	X	X	X	X	X	X		8.1.3

Table 1 Schedule of Activities (Phase 1 portion)

	Screening ^a	Cycle 0		Cycle 1				Cycle 2		Cycle 3	Cycle 4	Cycle 5-12		Cycles 15, 18, 21 and ≥ 24 ^b	EoT ^c	Safety Follow Up ^d	Post-treatment disease Follow up ^e	Survival Follow up ^f	Details in Section
		Single dose		Multiple doses															
Day of Each Cycle	-28 to -1	1	2	1	8	15	22	28	15	28	28	28	28	28					
Visit Window (Days)		0	0	0	±2	±2	±2	±2	±2	±2	±2	±2	±2	±3	+7	+7	± 7	± 7	

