Abbreviations: ALT = alanine aminotransferase; AST = aspartate aminotransferase; CR = complete remission; CT = computed tomography; ECG = electrocardiogram; ECOG = Eastern Cooperative Oncology Group; EoT = End of Treatment; GI = gastrointestinal; HBV = hepatitis B virus; HCV = hepatitis C virus; HIV = human immunodeficiency virus; Ig = immunoglobulin; IHC = immunohistochemistry; Lab = laboratory; LDH = lactate dehydrogenase; LTFU = long-term follow-up; mos = months; NK cell = Natural killer cell; PCR = polymerase chain reaction; PET = positron emission tomography; PK = pharmacokinetic; PS = performance status.

Footnotes (Phase 1 portion)

- a. Screening tests should be performed within 28 days before the first administration of study drug, unless otherwise indicated.
- b. Treatment with acalabrutinib may be continued until disease progression or any other treatment discontinuation criterion is met. After Cycle 24, subjects will continue to have scheduled visits every 12 weeks (± 3 days) as outlined on the schedule of activities.
- c. End of treatment visit will be done for subjects who permanently discontinue study drug for any reason, including disease progression. (except for death, lost to follow up or withdrawal of consent). The EoT visit should be performed within 7 days of the last dose of study drugs, if possible, and is not required for subjects who discontinue from study treatment within 10 days of a scheduled study visit or if the EoT visit would be performed within 14 days of the SFU visit.
- d. 30 day (+ 7 days) safety follow-up visit is required for all subjects after his or her last dose of study drug to monitor for AEs, regardless of whether the subject receives a new anticancer therapy or demonstrates disease progression within this timeframe.
- e. Post-treatment Disease Follow up is only required for R/R MCL subjects, who discontinue from study treatment due to reasons other than disease progression. Subjects will be followed approximately every 12 weeks from the date of last disease evaluation until disease progression, regardless of whether the subject receives a new anticancer therapy.
- f. Survival Follow up is only applicable for R/R MCL subjects who progress, but have not withdrawn consent. Subjects will be contacted approximately every 12 weeks by clinical visit or telephone until death or lost to follow up to assess survival and the use of alternative anticancer therapy.

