- g. Subjects should accept hospitalization at least from Cycle 0 Day -1 to Cycle 0 Day 2. Then, each subject may be discharged at an appropriate point on or after Cycle 0 Day 2 at the discretion of the investigator based on the result of assessment at discharge, which is the same as the test items performed at each pre-defined visit.
- h. The physical examination includes height (Screening only) and weight, and examination of the skin, eyes, ears, nose, throat, lungs, heart, abdomen, extremities, musculoskeletal, nervous, lymphatic system, and general appearance. The lymphatic system examination will include examination of palpable lymph nodes and spleen and liver below the costal margin on the respective side.
- i. Vital signs (Blood pressure, pulse rate, and body temperature) should be assessed after at least 5 minutes of rest for the subject in a quiet setting without distractions (e.g., television, cell phones).
- j. Twelve-lead ECGs will be obtained after the subject has been resting supine for at least 10 minutes before study-related ECGs. On the intensive PK sampling days (Cycle 0 Day 1 and Cycle 1 Day 8), the assessment will be performed at 1-2 hours post (morning) dose.
- k. Women of childbearing potential only. A urine or serum pregnancy test is acceptable. Pregnancy testing can be done more frequently than the protocol-defined schedule.
- l. Hematology includes complete blood count with differential and platelet counts.
- m. Clinical chemistry: albumin, alkaline phosphatase, Gamma glutamyl transferase (GGT), ALT, AST, urea or blood urea nitrogen (depending on local practice), calcium, chloride, creatinine, glucose, lactate dehydrogenase (LDH), magnesium, phosphate/phosphorus, potassium, sodium, total bilirubin, total protein, and uric acid, triglyceride, cholesterol.
- n. Hepatitis and HIV serology must include HBsAg, hepatitis B surface antibody (HBsAb), anti-HBc, hepatitis C (hepatitis C virus [HCV]) antibody and HIV antibody.

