- o. Subjects who are anti-HBc positive, HBsAg negative should have a quantitative PCR test for HBV DNA during screening and monthly basis from cycles 2 through 19. After Cycle 19, monitoring will occur every 3 months. HBV monitoring should continue until 12 months after last dose of study drug(s). Any subject with a rising viral load (above lower limit of detection) should discontinue study drug(s) and have antiviral therapy instituted and a consultation with a physician with expertise in managing hepatitis B. As intravenous immunoglobulins (IVIG) may cause false positive hepatitis serology, monthly PCR testing is not required in subjects who are currently receiving or received prophylactic IVIG within 3 months before study enrollment and have a documented negative anti-HBc test before the initiation of IVIG therapy. PCR testing should be performed when clinically indicated (e.g., in the setting of rising transaminase levels).

- p. Subjects with a known history of hepatitis C or who are hepatitis C antibody positive should have quantitative PCR testing for HCV RNA performed during screening. No further testing is necessary if the PCR results are negative at screening.
- q. Urinalysis: pH, ketones, specific gravity, bilirubin, protein, blood, and glucose.
- r. Testing will be done by central laboratory. T/B/NK cell count (i.e., CD3, CD4, CD8, CD19, CD16/56). During Cycles ≥ 5 , only done at the end of Cycles 6, 12, 18, and 24, then every 24 weeks thereafter.
- s. Serum immunoglobulin: IgG, IgM, IgA. During Cycles ≥ 5 , only done at the end of Cycles 6, 12, 18, and 24, then every 24 weeks thereafter.
- t. The indicated samples at this timepoint (Cycle 0 Day 1) must be drawn predose. If screening assessments chemistry, hematology, coagulation and urinalysis are performed within 5 days prior to Cycle 0 Day 1, they do not need to be repeated at Cycle 0 Day 1.

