- u. **CLL subjects should follow the CT frequency in Table 3.** For subjects other than CLL, a pre-treatment CT scan with contrast (unless contraindicated) is required of the neck, chest, abdomen, and pelvis and any other disease sites within 28 days before the first dose of study drug. During treatment, CT scans with contrast (unless contraindicated) will be performed for tumor assessments at the end of Cycle 2 (± 7 days), Cycle 4 (± 7 days), and Cycle 6 (± 7 days); then every 3 cycles (12 weeks, ± 7 days) thereafter, or more frequently at the investigator's discretion. Positron-emission tomography (PET)/CT scan is only required for MCL and DLBCL subjects. A pre-treatment PET-CT scan within 60 days from first dose of study drug is required. During treatment, PET-CT scans will be performed at the end of Cycle 2 (± 7 days) and Cycle 6 (± 7 days) as well as any time to confirm CR or as clinically indicated. Subjects with confirmed CR are not required to undergo further PET-CT scans on study unless there is suspicion of progressive disease in CT but cannot be proven, PET-CT may be used at the investigator's discretion. If GI tract involvement is suspected and supported by imaging, an endoscopy at baseline should be obtained. Endoscopy is required to confirm CR for any subjects with a documented history of gastrointestinal involvement. After confirmed CR, endoscopy is not mandatory for disease evaluation.
- v. Bone marrow aspiration and biopsy (including IHC) will be done at screening or within 60 days before the first dose of study drug per clinical guidelines. Bone marrow aspiration and biopsy will be performed any time to confirm CR (if bone marrow was involved by lymphoma at baseline) per clinical guidelines (see Section 8.1.1).
- w. PK samples are drawn per Section 8.5.1, and timepoints are relative to the first dose; predose, 0.25, 0.5, 0.75, 1, 2, 4, 6, 8, 12, 24 and 48 hours after the first dose. The 48 hours sample should be taken before the Cycle 1 Day 1 morning dose.
- x. PK samples are drawn per Section 8.5.1, and timepoints are relative to Cycle 1 Day 8 morning dose; predose, 0.25, 0.5, 0.75, 1, 2, 4, 6, 8 and 12 hours after morning dose. The 12 hours sample should be taken before the Cycle 1 Day 8 evening dose.
- y. PK samples are drawn per Section 8.5.1, and timepoints are relative to Cycle 1 Day 28 morning dose; 1, 2 and 4 hours after morning dose.

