1.2 Synopsis

National coordinating investigator:

PPD

[figure not shown]
Beijing City,

China.

Protocol Title: A Phase 1/2 Open Label, Multi-center Study to Assess the Safety, Tolerability, Pharmacokinetics and Clinical Efficacy of Acalabrutinib in Chinese Adult Subjects with Relapsed or Refractory Mantle Cell Lymphoma, Chronic Lymphocytic Leukemia or other B-cell Malignancies.

Rationale

CCI

Overall design

This is an open-label, two-part study to assess the safety, tolerability, pharmacokinetics and clinical efficacy of acalabrutinib in Chinese adult subjects with R/R MCL, R/R CLL or other B-cell malignancies. The study is divided into 2 parts: Phase 1 portion and Phase 2 portion.

Phase 1 portion

The primary objective of Phase 1 portion is to assess the safety, tolerability and pharmacokinetics of acalabrutinib in Chinese subjects with R/R B-cell malignancies and the secondary objective is to access the efficacy of acalabrutinib in Chinese subjects with R/R B-cell malignancies. Approximately 12 subjects will be enrolled in the Phase 1 portion. The study population includes subjects with R/R non-GCB diffuse large B-cell lymphoma (DLBCL), follicular lymphoma (FL), mantle cell lymphoma (MCL), chronic lymphocytic leukemia (CLL), small lymphocytic lymphoma (SLL).

Subjects will be administered a single dose of acalabrutinib 100 mg at Cycle 0 Day 1. During the following 2 days wash-out period, intensive PK samples will be collected before and after the first dose until pre-dose at Cycle 1 Day 1. From Cycle 1 Day 1, subjects will be administered multiple doses of acalabrutinib 100 mg BID on a continuous schedule (28 days per cycle). Intensive PK samples will be collected on Cycle 1 Day 8 for 12-hour PK profile at steady state. Additional sparse PK samples will be collected on Cycle 1 Day 28 to assess time-

dependent changes. Treatment with acalabrutinib may be continued for Cycle 2 onwards until disease progression or any other treatment discontinuation criterion is met. All subjects who discontinue the study drug will have a safety follow-up visit 30 (+7) days after the last dose of study drug.

The dose regimen of multiple doses of 100 mg BID has been found to be safe/tolerable and effective in overseas clinical studies in Western and Asian subjects. In case of intolerable toxicity, dose reduction to 100 mg QD may be considered (details in Section [6.6.2](#)).

Phase 2 portion

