To assess the efficacy of acalabrutinib in Chinese subjects with R/R CLL	ORR as assessed by BICR per iwCLL 2018 criteria
Phase 2 Portion Cohort B- Secondary Objective:	Endpoint/Variable:
To further assess the efficacy of acalabrutinib in Chinese subjects with R/R CLL	DoR, PFS and TTR as assessed by BICR per iwCLL 2018 criteria; ORR, DoR, PFS and TTR as assessed by investigators per iwCLL 2018 criteria; TTNT; CCI [REDACTED]
To assess the safety profile of acalabrutinib in Chinese subjects with R/R CLL	AEs, laboratory parameters, vital signs, and ECGs
To assess pharmacokinetics of acalabrutinib in Chinese subjects with R/R CLL	Plasma concentration of acalabrutinib (sparse sampling)
Safety Objectives are contained within the primary and secondary objectives.	

Data from R/R MCL subjects in both Phase 1 and Phase 2 will be combined for analysis.

Study Period

Study period		Phase of development
Estimated date of first subject enrolled	Q2, 2020	Phase 1 portion
Estimated date of last subject completed Phase 1 portion	Q2, 2022	Phase 1 portion
Estimated date of first subject enrolled Phase 2 portion	Q3, 2020	Phase 2 portion
Estimated date of last subject completed Phase 2 portion	Q4, 2023	Phase 2 portion

Number of Subjects

Approximately 12 Chinese subjects with R/R B-cell malignancies will be enrolled in Phase 1 portion. Approximately 33 Chinese subjects with R/R MCL (cohort A) and 60 Chinese subjects with R/R CLL (cohort B) will be enrolled in Phase 2 portion.

Treatments and treatment duration

In Phase 1 portion, all eligible subjects will first receive a single dose of acalabrutinib 100 mg and after 2 days washout period, the subjects will start to be treated at a continuous dosing of

[figure not shown]
acalabrutinib twice daily until disease progression or any other treatment discontinuation criteria is met.

In Phase 2 portion, all eligible subjects will be treated at a continuous dosing of acalabrutinib 100 mg BID until disease progression or any other treatment discontinuation criterion is met.

[figure not shown]
Statistical methods

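### In Phase 1 the repeat pregnancy test falls 48 hours after the first acalabrutinib dose, so the last required test before exposure can be 28 days old

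*Protocol*

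**What the plan says.** In the Phase 1 schedule (Protocol Section 1.1, Table 1), the pregnancy-test row has a mark at Screening, none at Cycle 0 Day 1 or Cycle 0 Day 2, and a mark at Cycle 1 Day 1. From then on it reads "As clinical indicated". The related provisions are:

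- **First dose.** The Synopsis states: "Subjects will be administered a single dose of acalabrutinib 100 mg at Cycle 0 Day 1". Section 8.1.3 likewise names Cycle 0 Day 1 as the Phase 1 first-dose day, and Cycle 1 Day 1 as that of Phase 2.
- **Interval to Cycle 1.** Table 1 footnote w: "The 48 hours sample should be taken before the Cycle 1 Day 1 morning dose".
- **Screening window.** Footnote a: "Screening tests should be performed within 28 days before the first administration of study drug, unless otherwise indicated".
- **Pregnancy test.** Footnote k: "A urine or serum pregnancy test is acceptable. Pregnancy testing can be done more frequently than the protocol-defined schedule".
- **Predose samples.** Footnote t requires the Cycle 0 Day 1 samples it marks to be drawn before the dose. It waives the repeat on one condition: "If screening assessments chemistry, hematology, coagulation and urinalysis are performed within 5 days prior to Cycle 0 Day 1". The pregnancy row does not carry this footnote.
- **Eligibility.** Inclusion criterion 19 asks for a negative test before enrolment and sets no limit on its age. Inclusion criterion 20 requires contraception from screening. Exclusion criterion 28 bars pregnant subjects.

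**The concern.** Pregnancy is an exclusion, so its check should be current at first exposure. In Phase 2 the screening test plus a Cycle 1 Day 1 test achieves this, because dosing starts that day. Phase 1 adds a Cycle 0 with a single dose. The other baseline laboratory tests are marked at Cycle 0 Day 1, but the pregnancy test is marked only at Cycle 1 Day 1.

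A woman whose pregnancy could not be detected at screening can therefore receive 100 mg of acalabrutinib before her next scheduled test. With a positive result before that dose she would be excluded unexposed, and Section 8.4.2 exempts a pregnancy found before any study drug from reporting. If it is found at Cycle 1 Day 1, it is an exposed pregnancy. Section 8.4.2.1 then requires discontinuation, notification within 24 hours and follow-up of the outcome.

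The point is one of patient safety. It does not touch any endpoint, sample size or error rate.

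**Working it through.** The plan states no figure on this point, so the check is a reading of the schedule, some day arithmetic and an illustration of size.

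**1. Column alignment.** Table 1 was extracted from a PDF, so the blanks need confirming. The columns after the row label run Screening, Cycle 0 Day 1, Cycle 0 Day 2, Cycle 1 Day 1, Cycle 1 Day 8.

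| Row | Screening | C0D1 | C0D2 | C1D1 |
|---|---|---|---|---|
| Hematology | X | X (footnote t) | blank | X |
| Pharmacokinetics | blank | X (w) | X (w) | X (w) |
| Pregnancy test | X | blank | blank | X |

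Footnote t names Cycle 0 Day 1. Footnote w covers predose to 48 hours after the first dose, and the next PK mark carries footnote x, which is Cycle 1 Day 8. Both rows fit the columns, so the pregnancy blanks are real.

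**2. Timing.** The first dose is at Cycle 0 Day 1, and the 48-hour PK sample is taken just before the Cycle 1 Day 1 dose. The repeat test day is therefore 48 hours after first exposure. Screening runs from Day -28 to Day -1 with no Day 0, so the screening test is 1 to 28 days old at the first dose. Phase 1 requires no pregnancy test on the first-dose day.

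**3. Comparison with Phase 2.** Seven laboratory rows in Table 2 (Cohort A) have a mark on the first-dose day: pregnancy, hematology, chemistry, coagulation, urinalysis, T/B/NK count and serum Ig. In Table 1 six of the seven are also marked at Cycle 0 Day 1; pregnancy is the exception. Table 3 (Cohort B) has the pregnancy test on its first-dose day.

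**4. Does another rule close the gap?** Inclusion 19 is satisfied by the screening test. Exclusion 28 sets a condition but no test. Footnote k permits extra tests and requires none. Footnote t's predose rule and 5-day limit do not cover the pregnancy test.

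**5. Size, simplest case.** Assume a constant conception rate of 1% per year; Table 5 defines highly effective contraception by a failure rate below that. The probability of conception over d days is 1 - 0.99^(d/365):

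- d = 1: 0.003%
- d = 5: 0.014%
- d = 28: 0.077%

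**6. Size, with a detection lag.** Contraception is required only from screening, and a test misses very recent conceptions. Let S be the age of the screening test in days and L the detection lag. Pregnancies negative at screening but positive at Cycle 0 Day 1 are those conceived between S + L and L days before dosing. That is a window of S days, of which min(L, S) fall before screening. The documents give neither L nor a pre-screening rate. I assume L of 0 to 14 days, 1% to 10% per year before screening, and 1% per year after. The corresponding daily hazards are 0.01005/365 at 1% and 0.10536/365 at 10%.

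- Low end (S = 1, L = 0): 0.003%.
- High end (S = 28, L = 14, 10% before screening): 1 - exp(-(14 × 0.10536 + 14 × 0.01005)/365) = 0.44%.
- If the pre-screening rate is also 1%, S = 28 gives 0.077% for any L.

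**7. Expected count.** If all 12 Phase 1 subjects were women of childbearing potential with 28-day-old tests, the expected number would be 12 × 0.077% ≈ 0.009, or 12 × 0.44% ≈ 0.05 at the high end. The actual number of such women is not given.

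**The case against.** The strongest reply concerns weight and timing.

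- **There may be nobody left to benefit.** The Synopsis row "Estimated date of last subject completed Phase 1 portion" gives Q2 2022. If completion there means the final Phase 1 data cut-off, about 14 months after the last enrolment in Phase 1 and Cohort A, then enrolment would have ended around February to April 2021. That is before protocol version 5.0 of 9 September 2021. The reading of completion is an inference, but the point stands: if Phase 1 dosing of new subjects has finished, no current subject gains.
- **Some comparators are weak.** T/B/NK count and serum Ig have no screening sample, so Cycle 0 Day 1 is their only baseline. The 5-day rule governs whether a baseline sample must be repeated; it is not a standard for how recent an eligibility test must be. Hepatitis and HIV serology may also be 28 days old. These points are fair, but they do not justify the gap: pregnancy status can change quickly after screening, and the protocol itself schedules a repeat test.
- **Other safeguards exist.** Contraception is required from screening, sites may test earlier, and exposure before the repeat test is limited to one 100 mg dose of a drug with a half-life of about 1 hour. All of this lowers the risk, but none of it requires a test before the first dose.
- **The high-end figure rests on assumed inputs.** The 14-day lag and the 10% rate are not in the documents. At 1% per year throughout, the figure does not exceed 0.077%.

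Nor is any written rule breached, since inclusion 19 sets no limit in days.

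**Conclusion.** The concern holds. Following Table 1 exactly, the Phase 1 repeat pregnancy test comes 48 hours after first exposure, and the last required test before the dose is 1 to 28 days old. This is a misplaced check rather than missing detail.

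The expected number of exposures averted is well below one even under the least favourable assumptions, and the documents contain no basis for judging the harm of a single dose in pregnancy. The case for change rests on its small cost rather than on a large risk. The Phase 2 pregnancy rows also carry no explicit predose mark, so the contrast is with a test on the first-dose day, not with a guaranteed predose one.

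**What to change.** In Table 1, move the pregnancy-test mark from Cycle 1 Day 1 to Cycle 0 Day 1 predose, or to Day -1 at admission. Add one sentence to footnote k saying that the result must be negative before the first dose is given. The last required test would then be 0 days old at first exposure, or 1 day old with the Day -1 option, instead of up to 28.

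The number of tests and visits does not change. Footnote g already has subjects in hospital ("Subjects should accept hospitalization at least from Cycle 0 Day -1 to Cycle 0 Day 2"), and predose samples are already due at Cycle 0 Day 1. The cost is a minor amendment with IRB/IEC approval under Appendix A 1. If Phase 1 dosing of new subjects has ended, an amendment to this protocol brings no benefit, and the correction should be made wherever the schedule is reused.
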